14.3.5 Time to Disease Progression

Time to disease progression (TTP) will be calculated in the same fashion as described for PFS with the exception that for subjects who die for causes other than disease progression, TTP will be censored at the date of the other cause mortality. Otherwise, the censoring mechanism for TTP will be the same as previously described for PFS.

14.3.6 Duration of Response

Duration of response (DoR) will be calculated for each subject with response for the VGPR+ and overall response endpoints. The DoR intervals will be calculated from the time of the first assessment that identified response until disease progression or death. The censoring mechanism for DoR will be the same as described for PFS.

14.3.7 Time to Next Treatment

Time to next treatment (TTNT) will be calculated from the time of treatment start until the start of the first subsequent anti-cancer therapy after all protocol directed therapy is completed. For surviving subjects who do not receive subsequent therapy, TTNT will be censored at the last contact date. For subjects who die before beginning subsequent anti-cancer therapy, TTNT will be censored at the date of death.

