The combination of carfilzomib (Kyprolis®) with lenalidomide (Revlimid®) and dexamethasone (a regimen termed “KRd”) initially exhibited excellent clinical activity in a phase Ib/II clinical trial in relapsed/refractory MM patients. In the dose escalation portion of the study (n=40), no maximally tolerated dose (MTD) was identified, and the maximum planned dose (MPD; 27mg/m² of carfilzomib) was recommended for the phase II portion (with an initial dose of 20mg/m² on days 1 and 2 of cycle 1, with the overall dosing regimen defined as 20/27 mg/m²). The overall response rate (ORR) across the dose escalating cohorts was 62.5% [5]. In the phase II portion, 52 patients were enrolled and treated with the combination at the MPD for carfilzomib. The ORR in this cohort was 76.9% (the very good partial response or better [VGPR+] rate was 42.3%) and the median PFS was 15.4 months [6].

This trial was followed by the open-label phase III trial, ASPIRE, wherein KRd was compared to Rd in patients with relapsed/refractory MM (1-3 prior lines of therapy). Median PFS was significantly improved with the triplet (26.3 months compared to 17.6 months, $p=0.0001$), as was the VGPR+ rate (69.9% compared to 40.4%). Median OS was not yet reached at the time of the analysis, but the OS rate at 24 months favored the triplet (73.3% versus 65%, $p=0.04$). Notably, patients in the KRd arm reported better quality of life as compared to the Rd arm [7]. This trial led to the Food and Drug Administration (FDA) approval of carfilzomib in combination with Rd for the treatment of patients with relapsed or refractory MM.

[figure not shown]

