14.5 Analysis Methods

14.5.1 Timing of Analysis

The primary analysis will occur after VGPR+ status (yes or no) has been determined for all subjects. Secondary endpoints will also be assessed at the time of the primary analyses. Updated analyses will be conducted after the PFS censoring rate reaches 20% or when all surviving subjects who are not lost to follow up or have not been withdrawn from the study have been on study for at least 3 years, whichever occurs first. A final analysis will be conducted after the overall survival censoring rate reaches 20% or after all surviving subjects who are not lost to follow up or have not been withdrawn from the study have been on study for at least 5 years, whichever occurs first.

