14.5.5 Secondary Analysis

The frequencies and proportions of overall response will be calculated. Corresponding 95% confidence intervals will be estimated using the Clopper-Pearson method. OS, PFS, TTP, TTNT, and DoR endpoints will be analyzed using Kaplan Meier techniques. Selected landmarks will be estimated and reported. Logistic regression models and Cox proportional hazards models will be used to analyze the treatment response endpoints as functions of baseline subject and disease characteristics, and results from biomarker studies as previously described. The percent of subjects achieving MRD negative status will be summarized. Subgroup analyses will be conducted for selected efficacy endpoints on the subset of MRD negative subjects (i.e. time to event endpoints).

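### TTNT is censored at death and summarised by Kaplan-Meier, so one minus the curve overestimates the probability of starting next treatment and the curve is not treatment-free survival either

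*Combined protocol and SAP*

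**What the plan says.** Section 14.3.7 sets the clock and the event: "Time to next treatment (TTNT) will be calculated from the time of treatment start until the start of the first subsequent anti-cancer therapy". Death is not part of the event, and the secondary objective in Section 2.2 defines TTNT the same way.

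Two groups are censored. For those alive: "For surviving subjects who do not receive subsequent therapy, TTNT will be censored at the last contact date". For those who have died: "For subjects who die before beginning subsequent anti-cancer therapy, TTNT will be censored at the date of death". Both enter the analysis with the same status.

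The estimator is in Section 14.5.5: "OS, PFS, TTP, TTNT, and DoR endpoints will be analyzed using Kaplan Meier techniques". The statistical section names no cumulative incidence, no competing-risk method, and no endpoint that combines next treatment with death.

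Section 14.3.5 has a parallel rule for deaths not due to progression: "TTP will be censored at the date of the other cause mortality". Section 14.3.4 defines PFS with death as an event.

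Under Section 14.5.1 the final analysis waits for OS censoring to fall to 20% or until survivors "have been on study for at least 5 years, whichever occurs first". Deaths before next treatment therefore have time to accrue.

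**The concern.** Kaplan-Meier treats a censored subject as someone whose later rate of starting therapy is the same as that of subjects still under observation. That is reasonable for a survivor at last contact. It is not reasonable for a subject who has died, whose later rate is zero.

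The resulting curve answers neither question a reader would bring to it. One minus the curve is not the proportion of subjects who go on to next treatment. The curve itself is not the proportion alive and free of next treatment. The median lies between the medians for those two quantities, at a distance set by how many subjects die first.

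In a single-arm trial TTNT will be read against published figures, and no concurrent arm carries the same distortion. Progression has PFS as a death-inclusive companion to TTP. TTNT has no such companion in the plan.

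**Working it through.** The documents give no expected value, event count or precision for TTNT, so there is no planned figure to reproduce. The check compares three quantities under constant hazards.

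**Inputs**
- m, the median time to next treatment or death. It is not in the documents. As an assumed scale I use the two historical KRd PFS medians in Section 1.2: 15.4 months ("the median PFS was 15.4 months", phase II) and 26.3 months (phase III). PFS counts death, so it is matched to the treatment-or-death composite and not to treatment alone.
- s, the share of first events that are deaths. It is not in the documents and is assumed at 5%, 10%, 20% and 30%.

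**Formulas**, with total hazard L = ln 2 / m
- Treatment or death: median m; probability by t is 1 − exp(−Lt).
- Planned Kaplan-Meier with death censored: median ln 2 / [L(1 − s)] = m / (1 − s); one minus the curve at t is 1 − exp(−L(1 − s)t).
- Cumulative incidence of next treatment: (1 − s)[1 − exp(−Lt)]; it reaches 50% at −ln[1 − 0.5/(1 − s)] / L.

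**Worked case**, m = 15.4, s = 20%
- L = 0.6931 / 15.4 = 0.0450 per month.
- Kaplan-Meier median = 15.4 / 0.8 = 19.3 months.
- Cumulative-incidence median = −ln(1 − 0.625) / 0.0450 = 21.8 months.
- At 36 months: 1 − exp(−0.0450 × 0.8 × 36) = 72.6%; 0.8 × [1 − exp(−0.0450 × 36)] = 64.2%; 1 − exp(−0.0450 × 36) = 80.2%.

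**All cases**

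| m (months) | s | KM median | Cumulative-incidence median | 36-month 1−KM | 36-month cumulative incidence | 36-month treatment or death |
|---|---|---|---|---|---|---|
| 15.4 | 5% | 16.2 | 16.6 | 78.5% | 76.2% | 80.2% |
| 15.4 | 10% | 17.1 | 18.0 | 76.7% | 72.2% | 80.2% |
| 15.4 | 20% | 19.3 | 21.8 | 72.6% | 64.2% | 80.2% |
| 15.4 | 30% | 22.0 | 27.8 | 67.8% | 56.2% | 80.2% |
| 26.3 | 5% | 27.7 | 28.4 | 59.4% | 58.2% | 61.3% |
| 26.3 | 10% | 29.2 | 30.8 | 57.4% | 55.2% | 61.3% |
| 26.3 | 20% | 32.9 | 37.2 | 53.2% | 49.0% | 61.3% |
| 26.3 | 30% | 37.6 | 47.5 | 48.5% | 42.9% | 61.3% |

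The ratio of the Kaplan-Meier median to the treatment-or-death median is 1/(1 − s) whatever m is: 1/0.95 = 1.05 at 5% deaths and 1/0.70 = 1.43 at 30%. Against the cumulative incidence, the Kaplan-Meier median is short by 0.4 to 5.8 months for m = 15.4 and by 0.7 to 9.9 months for m = 26.3.

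**Simulation check** (n = 40, 4,000 replicates, m = 20 months, 36 months, Aalen-Johansen against Kaplan-Meier). Mean 1−KM / cumulative incidence / composite was 67.5 / 64.2 / 71.3% at s = 10%, 63.2 / 57.1 / 71.3% at 20%, and 58.5 / 50.1 / 71.5% at 30%. The ordering is the same.

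**The case against.** The best case for leaving the plan alone has four parts.

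**Low stakes.** TTNT is a descriptive secondary estimate with no test, threshold or decision attached. This stands.

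**Deaths are visible elsewhere.** OS, PFS and DoR count death, and deaths on study therapy are summarised as a safety endpoint (Sections 14.3.8 and 14.5.6). This also stands, and it settles TTP: censoring other-cause death is what distinguishes TTP from PFS, and PFS already supplies the death-inclusive version. It does not settle TTNT, which has no such counterpart.

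**Size.** The death share is assumed, and 40 subjects give wide intervals. At 72.6%, a simple binomial 95% half-width is 1.96 × √(0.726 × 0.274 / 40), about 14 percentage points, against a gap of 72.6 − 64.2 = 8.4 points. That is fair as to scale. However, the interval reflects chance around whatever is being estimated and does not correct a systematic shift.

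**Changing the endpoint.** Counting death as an event would redefine the secondary objective in Section 2.2. This is right, and it is why the composite belongs only in a labelled supplement.

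A reader might also infer that the plan keeps dead subjects as still awaiting treatment and so overstates TTNT. The documents do not support that. Censoring removes them from the risk set; it is the cumulative incidence that keeps them as never treated. For TTNT as Sections 2.2 and 14.3.7 define it, the Kaplan-Meier time is too short. It is too long only against a treatment-or-death composite that the protocol does not define.

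**Conclusion.** The point holds for TTNT. Censoring at death under Kaplan-Meier gives a one-minus-survival figure that is too high as a probability of next treatment, and a curve that is not treatment-free survival. For deaths at 5% to 30% of first events, with constant hazards, the Kaplan-Meier median is about 5% to 43% above the treatment-or-death median and below the cumulative-incidence median. In the table, the 36-month overestimate of next-treatment probability runs from 1.2 points (59.4 − 58.2) to 11.6 points (67.8 − 56.2). These sizes rest on the assumed death share, the constant hazards and PFS medians borrowed as a time scale. The ordering does not depend on the particular values chosen.

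It might be inferred that an early toxic death makes the reported median TTNT look better. That is true only relative to counting the death as an event. Under the plan such a subject simply leaves the risk set, and with constant hazards the expected curve for next treatment does not move.

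The effect is confined to a descriptive secondary endpoint. TTP can stay as planned, and the VGPR+ test in Sections 14.2 and 14.5.4 is untouched.

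**What to change.** - **Section 14.5.5:** estimate TTNT, as already defined, by the Aalen-Johansen cumulative incidence of next treatment, with death before next treatment as a competing event. Survivors without next treatment remain censored at last contact.
- **Section 14.3.7:** replace censoring at death with a statement that death before next therapy is a competing event.
- **Supplement:** report Kaplan-Meier time to next treatment or death under that name, so that it is not mistaken for TTNT.
- **Reporting:** give the number of subjects who die before next treatment, so that readers can judge how far the two summaries differ.

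No new data are needed: dates of death and of next therapy are already required for OS and TTNT. The cost is a short wording change and a little extra analysis with standard software. The two summaries move in opposite directions from the planned one, since the cumulative-incidence median is longer and the treatment-or-death median shorter. Both should therefore be fixed in the text before the data are analysed.

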14.3.8 Safety Endpoints

Safety endpoints will include treatment administration (cumulative dose, dose intensity, and relative dose intensity—dose intensity as a percent of intended dose intensity), AEs, SAEs, and deaths while on study therapy.

14.4 Analysis Populations

Analyses of response endpoints (response evaluable population) will be conducted on the population of subjects who initiate treatment with elotuzumab and who have measurable disease at baseline. Analyses of other efficacy and safety endpoints will be conducted on the population of subjects who initiate treatment with elotuzumab. Exploratory analyses will be conducted on the population of subjects who initiate treatment with elotuzumab treatment and who have available biomarker data.

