3.4 Screen Failures

A subject who, for any reason (e.g., failure to satisfy the selection criteria or withdraws consent), terminates his/her study participation before receiving the first dose of study therapy is regarded as a “screen failure.” All screen failures will be tracked. Enrollment will continue until the targeted sample size in the evaluable population (Section 14.4) is achieved.

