5.1 KRd+Elotuzumab Induction Regimen

All subjects enrolled will receive KRd+elotuzumab induction. See Section 6 for details on drug administration and dose modifications/delays. **NOTE:** Pre-hydration is required for carfilzomib as described in Section 6.3.2 and premedication is required prior to elotuzumab as described in Section 6.4.1.

Table 1: KRd+Elotuzumab Induction Regimen

Drug	Dose	Route	Schedule	4-Week (28D) Cycle
Carfilzomib ^{a,b}	20 mg/m ²	IV	D1	Cycle 1
Carfilzomib ^{a,b,c}	56 mg/m ²	IV	D8, 15	Cycle 1
Carfilzomib ^{a,b,c}	56 mg/m ²	IV	D1, 8, 15	Cycles 2-4
Lenalidomide	25 mg ^d	Oral	Once a day at bedtime on D1-21	Cycles 1-4
Dexamethasone ^g	28 mg	Oral	Once weekly ^e on D1, 8, 15, 22	Cycles 1-2
	8 mg	IV		
Dexamethasone ^{e,g}	28 mg	Oral	D1	Cycles 3-4
	8 mg	IV		
Dexamethasone ^{f,g}	40 mg	PO	Once weekly on D8, 15 and 22	Cycles 3-4
Elotuzumab ^b	10 mg/kg	IV	Once weekly on D1, 8, 15, 22	Cycles 1-2
Elotuzumab ^b	20 mg/kg	IV	D1	Cycles 3-4

^a Calculate the dose using the subject's actual body surface area (BSA) at baseline. For subjects with a BSA >2.2m², calculate the dose based upon a BSA of 2.2m².

^b If a subject's weight changes by more than 10% from induction cycle 1 day 1 the dose of carfilzomib and elotuzumab should be recalculated. This re-calculated weight should be used as the new baseline weight. **NOTE:** use the subject's actual (not ideal) body weight for dosing as per the American Society of Clinical Oncology (ASCO) guidelines in dosing of obese adult subjects.

^c **NOTE:** In subjects who enroll with a bilirubin and/or AST >1 x ULN, the starting dose of carfilzomib of 20mg/m² should be maintained and not increased to 56mg/m². The dose may be escalated to 56 mg/m² if both bilirubin and AST resolve to ≤ ULN.

^d For subjects who enroll with a CrCl between 40-50 mL/min, the starting dose of lenalidomide may be reduced to 10mg at the discretion of the investigator.

^e On days when elotuzumab is administered: 28mg PO between 3-24 hours prior to start of elotuzumab **OR** as a split dose of 12 mg 12-24 hours and 16 mg 3 hours prior to elotuzumab; 8 mg IV 45 to 90 minutes prior to elotuzumab infusion. **NOTE:** This will serve as the corticosteroid premedication for elotuzumab on days when elotuzumab is administered during induction

^f May administer 20 mg dexamethasone for subjects ≥ 75 years old

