6. TREATMENT DETAILS AND DOSE MODIFICATIONS/DELAYS

Any subject who receives treatment on this protocol will be evaluable for toxicity. Each subject will be assessed periodically for the development of any toxicity according to the Study Calendar. Toxicity will be assessed according to the National Cancer Institute (NCI) Common Terminology Criteria for Adverse Events (CTCAE), v4.03. Dose adjustments should be made according to the system showing the greatest degree of toxicity.

Note: In each dose modification table in Section 6, the Recommended Action is per investigator's discretion.

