6.3 Carfilzomib

6.3.1 Administration

Subjects with active or suspected infection of any kind that require systemic treatment should not be dosed with carfilzomib until the infection has resolved and if being treated with an anti-infective(s), the course of antibiotics has been completed.

Subjects will receive carfilzomib as an intravenous (IV) infusion over approximately 30 minutes as per the dose and schedule outlined in Table 1 for induction. If the subject has a dedicated line for carfilzomib administration, the line must be flushed with a minimum of 20 mL of normal saline prior to and after drug administration. The dose must be administered at a facility capable of managing IRRs.

On the days both carfilzomib and elotuzumab are due to be administered, carfilzomib will be administered first.

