14.1.2 Enrollment (On Study) Date

The date of initiation of study treatment on Cycle 1, Day 1.

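### Section 14.4 admits subjects to the safety and time-to-event analyses only once elotuzumab starts, so a treated subject who never receives it is enrolled but in no analysis set

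*Combined protocol and SAP*

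**What the plan says.** Section 14.4 uses one entry condition throughout. The response-evaluable set is the "population of subjects who initiate treatment with elotuzumab and who have measurable disease at baseline". For everything else, "Analyses of other efficacy and safety endpoints will be conducted on the population of subjects who initiate treatment with elotuzumab". The exploratory set also requires elotuzumab, plus biomarker data. Section 14.5.6 (Safety Analysis) names no other population, so 14.4 governs the safety tables.

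Other sections are framed around the whole regimen:

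- Section 6: "Any subject who receives treatment on this protocol will be evaluable for toxicity".
- Section 14.1.2 sets the enrollment date as "The date of initiation of study treatment on Cycle 1, Day 1".
- Section 14.5.6 defines treatment-emergent events relative to treatment start, and summarises carfilzomib and lenalidomide exposure as well as elotuzumab.
- Section 3.4 limits screen failures to subjects who leave before any study therapy is given, and adds: "Enrollment will continue until the targeted sample size in the evaluable population (Section 14.4) is achieved".

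On the order of drugs, Section 6.3.1 says: "On the days both carfilzomib and elotuzumab are due to be administered, carfilzomib will be administered first". Footnote e to Table 1 (Section 5.1) puts oral dexamethasone at "28mg PO between 3-24 hours prior to start of elotuzumab" (or as a split dose) and IV dexamethasone at "8 mg IV 45 to 90 minutes prior to elotuzumab infusion".

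**The concern.** A safety population normally contains everyone exposed to the regimen. Here it is defined by the last of the drugs administered at the first infusion visit. Between the first protocol drug and the start of elotuzumab a subject is exposed to dexamethasone and carfilzomib. The protocol's own drug information (Section 10.2.5) says that carfilzomib infusion reactions can be immediate and life-threatening, and that death from cardiac arrest has occurred within one day of a dose. Whether the subject goes on to elotuzumab can therefore depend on a toxicity of the regimen being studied.

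If such a subject never starts elotuzumab, following 14.4 exactly leaves that subject out of the summaries of adverse events, SAEs, deaths on therapy and exposure, and out of OS, PFS, TTP and TTNT. Section 3.4 then enrols a replacement. What is at stake is mainly the completeness of the safety tables of a small single-arm study of a new four-drug combination.

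**Working it through.** **1. Trace one subject.** Suppose a subject receives dexamethasone and carfilzomib on Cycle 1 Day 1 and never starts elotuzumab.

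| Question | Section | Answer |
|---|---|---|
| Screen failure? | 3.4 | No, study therapy has been given |
| Enrolled? | 14.1.2 | Yes, study treatment began on Cycle 1 Day 1 |
| Evaluable for toxicity? | 6 | Yes |
| AEs and SAEs collected? | 12.3.1, 12.3.3 | Yes, from Day 1 and from consent respectively |
| In the disposition summary? | 14.5.2 | Yes, it covers all consenting subjects |
| In the safety set? | 14.4 | No |
| In the OS, PFS, TTP and TTNT set? | 14.4 | No |
| In the response-evaluable set? | 14.4 | No |
| Replaced? | 3.4 | Yes, enrolment runs to the 14.4 target |

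The Section 6 and Section 14.4 rows contradict each other.

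**2. The plan's own figures (Section 14.2).** Inputs: null 40%, alternative 60%, one-sided alpha 0.10, power 90%, N = 40, reject at 21 or more.

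- Normal approximation: n = (1.2816 + 1.2816)² × 0.24 / 0.20² = 39.4, rounded up to 40. Power at 40 = Φ(0.20 × √40 / √0.24 − 1.2816) = 90.3%. The stated N and power are reproduced.
- Exact binomial for the 21/40 rule: P(X ≥ 21 | 40, 0.40) = 0.074 and P(X ≥ 21 | 40, 0.60) = 0.870. The gap between 87.0% and 90% is a separate matter and does not bear on this point.

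**3. Safety tables.** Let k be the number of treated subjects who never start elotuzumab. The documents do not give k; I assume 0 to 2. Take an event seen only in these k subjects, with 40 others in the 14.4 set. Intervals are two-sided 95% Clopper-Pearson.

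| k | Reported under 14.4 | All treated |
|---|---|---|
| 1 | 0/40 (upper limit 8.8%) | 1/41 = 2.4% (0.1% to 12.9%) |
| 2 | 0/40 (upper limit 8.8%) | 2/42 = 4.8% (0.6% to 16.2%) |

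The upper limit for 0/40 is 1 − 0.025^(1/40) = 8.8%.

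**4. Primary endpoint.** Count the k subjects as non-responders and hold responders at exactly 21. The exact one-sided p is P(X ≥ 21 | 40 + k, 0.40).

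| k | VGPR+ | p | Below 0.10? |
|---|---|---|---|
| 0 | 21/40 = 52.5% | 0.074 | Yes |
| 1 | 21/41 = 51.2% | 0.097 | Yes |
| 2 | 21/42 = 50.0% | 0.122 | No |

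So the conclusion changes only when the result sits exactly on the 21-responder boundary and at least two subjects are affected.

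**The case against.** Three stronger readings are tempting, and the documents do not support them.

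*Anyone harmed before the first elotuzumab infusion drops out.* Only subjects who never start elotuzumab are lost. Under Table 9 (Section 6.4.3) a missed weekly dose resumes at the next planned weekly date. A subject who receives it then enters the 14.4 safety set with the Day 1 event. Also, the carfilzomib first-dose effect in Section 6.3.3 is described as arising in the evening after the first infusion, which would usually be after that day's elotuzumab.

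*Serious toxicity disappears.* It does not leave the record. SAEs go to the Sponsor-Investigator, the manufacturer and the IRB (Sections 12.3.3 to 12.3.4), and a death would appear in disposition. What is lost is the count in the 14.5.6 summaries.

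*VGPR+ is biased upward and the test is unsafe.* The null hypothesis in Section 14.2 concerns subjects treated with elotuzumab plus KRd, and a subject who never had elotuzumab did not receive that combination. The response-evaluable set requires no post-baseline assessment, so it already keeps early deaths and dropouts after elotuzumab starts. There is an upward effect only against an any-drug target, and nothing in the documents suggests that two such subjects should be expected.

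The sponsor could add that elotuzumab is the defining drug: Section 14.1.3 dates treatment discontinuation from the decision to stop it. That supports the response-evaluable set. It does not explain a safety set at odds with Section 6, or a treatment-emergent definition and exposure summaries that cover the regimen. The conflict over safety stands.

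**Conclusion.** The inconsistency is real and narrow. Section 14.4, read as written, excludes from every analysis set a subject who is enrolled, treated and evaluable for toxicity under other sections, and Section 3.4 replaces that subject. This applies only to subjects who never receive elotuzumab.

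For safety, each such subject is 1 of about 41 treated (2.4%), and an event confined to that subject would be tabulated as 0/40. For efficacy the effect is hypothetical: one such subject leaves a 21-responder result significant, and two would not. The range of 0 to 2 is an assumption, and the true number may be zero. The point is worth correcting because it completes the safety reporting and removes a contradiction at almost no cost. It does not call the primary test into question.

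**What to change.** In Section 14.4:

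- Define the safety population as all subjects who receive at least one dose of any protocol drug (dexamethasone, carfilzomib, lenalidomide or elotuzumab). Use the same set for OS, PFS, TTP and TTNT, which are measured from treatment start.
- Anchor the set and the time origin to study treatment begun on or after Cycle 1 Day 1. Oral dexamethasone may be taken up to 24 hours before elotuzumab, so possibly on the previous day, while enrollment and non-serious AE collection begin on Day 1. List separately, with any SAEs, a subject who took only pre-Day-1 oral dexamethasone.
- Keep the response-evaluable set and the 21/40 rule for the primary test.
- Add one supplementary row giving VGPR+ in all treated subjects, with unassessed subjects counted as non-responders.

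This brings 14.4 into line with Sections 6, 14.1.2 and 14.5.6. The cost is a change of wording and one extra table row; the data are already collected from Day 1. The VGPR+ rate in the added row may be slightly lower than the primary figure. If no such subject exists, no result changes.
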